In a recently completed study (POC) (13), we found that not correcting mild to moderate hyperglycemia at bedtime did not change fasting daily glucose levels (Figure 6). Further, there were no changes in mean daily glucose, pre-meal glucose or hypoglycemic events (Figure 7). In this study, TDD of insulin was 42 units/day. Of this, only 6 units/day was required as a supplemental dose.

**Frequency of hypoglycemia and hyperglycemia during basal insulin treatment.** The frequency of mild hypoglycemia (BG<70 mg/dl) and severe hypoglycemia (BG<40 mg/dl) at bedtime among 2,377 patients recruited in different randomized control trials conducted by our research team is less than 1.5% and 0.5%, respectively. The frequency of hypoglycemia is low in comparison to patients treated with sulfonylureas (26). Similarly, the frequency of severe hyperglycemia (BG>400 mg/dl) is remarkably low (0.08%) among insulin treated patients with T2DM (6; 7).

*In summary*, during the past decade our research group has provided novel and important information to guide health care providers in inpatient management of patients with hyperglycemia and diabetes. Our preliminary data indicate that the use of basal insulin alone or in combination with rapid-acting insulin analogs (basal bolus regimen) in non-ICU patients with T2DM improves glycemic control and reduces the rate of hypoglycemia. In addition, our studies

have shown that BG values remain relatively constant during the day and that the need for supplemental insulin is low in comparison to the TDD of insulin required.

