**BEDTIME. Give half of Supplemental Sliding Scale Insulin.**

Blood Glucose (mg/dL)	Sensitive	Usual	Resistant
<221	0	0	0
221-260	1	2	4
261-300	2	3	5
301-350	3	4	6
351-400	4	5	7
> 400	5	6	8

The patient's inpatient primary medical or surgical team may change insulin dose at their discretion in the presence of hypoglycemia (BG <70 mg/dL) or severe hyperglycemia (BG >350 mg/dL). In addition, the attending and/or study physician may consider using the total supplemental insulin dose, patient's nutritional intake, and results of BG testing to adjust insulin regimen.

**Blood glucose monitoring.** BG will be measured before each meal, at bedtime and/or 3 AM (or every 6 hours if a patient is not eating) using a glucose meter. In addition, blood glucose will be measured at any time if a patient experiences symptoms of hypoglycemia or if requested by the treating physician. The nursing staff or a research team staff will record all glucose readings in the hospital's blood glucose flow-sheet (electronic chart).

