## **VI. CLINICAL MANAGEMENT GUIDELINES**

**V.I.a. Treatment of Hypoglycemia.** Hypoglycemia, defined as a BG level < 70 mg/dL will be treated following standard hypoglycemia protocols available at our institutions (6; 7; 29).

**V.I.b. Assessment and Monitoring of Hospital Complications and Mortality.** The research team will follow patients daily in order to determine presence of infectious and non-infectious complications. Nosocomial infections will be diagnosed based on standardized CDC criteria (30).

**VII. Data Analysis.** The primary endpoint of this study is mean fasting BG concentration between treatment groups. We set the equivalence margin in our non-inferiority hypothesis for comparing treatment effect as 18 mg/dL (1 mmol/l). Based on previous studies (6; 7), we anticipate a standard deviation of mean fasting BG~50 mg/dL. With a one-sided, two-sample t-test, 123 subjects would be required for each group to achieve 80% power to detect non-inferiority. Here we conservatively set the significance level as 0.025 to ensure sufficient power when a two-sided test is used for the primary outcome, we will perform cross-sectional analyses using one-way ANOVA or linear models, followed by repeated measures ANOVA or linear models to estimate difference between treatment groups while simultaneously examining mean fasting BG across multiple days during treatment. Similar analyses will be conducted for continuous secondary outcomes. Chi-square tests (or Fisher's Exact test), Logistic regression, and Poisson regression will be conducted to analyzed discrete secondary outcomes. A p-value of <0.05 is considered significant. We expect a very low attrition rate in the proposed study. Therefore, a total of 250

patients (125 patients per group) will be recruited in this pilot study. The proposed methods will be implemented by SAS (v9.2).

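### The only non-inferiority test is on fasting BG, but the arms differ mainly in correction before meals, so a loss of daytime control could pass it

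*Combined protocol and SAP*

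**What the plan says.** Section VII states: "The primary endpoint of this study is mean fasting BG concentration between treatment groups". The 18 mg/dL margin, the SD and the sample size all attach to that endpoint: "we anticipate a standard deviation of mean fasting BG~50 mg/dL", and "With a one-sided, two-sample t-test, 123 subjects would be required for each group to achieve 80% power to detect non-inferiority". The planned models keep to it as well, estimating the arm difference while "simultaneously examining mean fasting BG across multiple days during treatment". No other outcome has a margin. Section IV.b, by contrast, names mean daily BG as the primary outcome and lists mean BG before meals, at bedtime and at 3 AM as secondary outcome 1.

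The treatment contrast is set by the supplemental scales in IV.d. Before meals, Group 1 is corrected from BG 141 upward and Group 2 only above 260. At bedtime each group has its own table under the heading "BEDTIME. Give half of Supplemental Sliding Scale Insulin", and the two tables agree in every row except 221-260. The insulin adjustment rules are the same in both groups: basal insulin is raised, or total insulin lowered, according to fasting and/or pre-dinner BG, with 100-140 mg/dL as the target.

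The Preliminary Data report from an earlier trial by the same group that "not correcting mild to moderate hyperglycemia at bedtime did not change fasting daily glucose levels".

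**The concern.** The trial asks whether correction of mild to moderate hyperglycemia can be left out. A dose before breakfast, lunch or dinner bears first on the next reading: pre-lunch, pre-dinner or bedtime. The fasting reading comes after the bedtime dose, where the two scales are nearly the same. Shared titration narrows the fasting contrast further, because a high pre-dinner BG in Group 2 raises basal insulin, which may lower the next fasting value while the daytime loss remains.

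A non-inferior fasting result could therefore be read as showing that pre-meal correction is unnecessary, although the readings that those doses act on had become worse. The time-of-day means in secondary outcome 1 would be examined, but only at p<0.05 and without a margin. A non-significant difference there does not exclude a loss of 18 mg/dL.

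**Working it through.** **Step 1. The plan's own figure.** Inputs from VII: margin 18, SD 50, power 80%, and "Here we conservatively set the significance level as 0.025". A true difference of 0 is assumed; VII does not state it. Normal approximation: n = 2 × 50² × (1.960 + 0.842)² / 18² = 121.1, so 122 per group. With the noncentral t, power is 0.7997 at 122 and 0.8029 at 123. The stated 123 reproduces. At the 125 to be recruited, power is 0.809. The arithmetic is sound; the question is what is being tested.

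**Step 2. Where the arms differ.** Group 1 minus Group 2, units per dose, from the four tables in IV.d (sensitive / usual / resistant):

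| BG (mg/dL) | Before each meal | Bedtime |
|---|---|---|
| 141-180 | 2 / 3 / 4 | 0 / 0 / 0 |
| 181-220 | 3 / 4 / 6 | 0 / 0 / 0 |
| 221-260 | 4 / 5 / 8 | 1 / 2 / 4 |
| 261 and above | 0 / 0 / 0 | 0 / 0 / 0 |

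The largest contrast on the usual scale is 3 × 5 = 15 units a day before meals, against 2 units at bedtime.

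**Step 3. What the fasting test would miss.** Let D be the true rise in Group 2 at the pre-lunch, pre-dinner and bedtime readings, and f the share of D that reaches the fasting reading. The documents do not give f, so a range is shown. At 125 per group the standard error is 50 × √(2/125) = 6.32. The 95% half-width is 1.970 × 6.32 = 12.5, so non-inferiority needs an observed difference below 18 − 12.5 = 5.5. The probability of declaring it comes from the noncentral t with 248 degrees of freedom and noncentrality (18 − f × D)/6.32:

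| f | Fasting difference, D = 18 | P(non-inferior), D = 18 | P(non-inferior), D = 36 |
|---|---|---|---|
| 0% | 0 | 0.81 | 0.81 |
| 10% | 1.8 | 0.72 | 0.62 |
| 25% | 4.5 | 0.57 | 0.29 |
| 50% | 9.0 | 0.29 | 0.025 |
| 100% | 18.0 | 0.025 | <0.001 |

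**Step 4. The same loss on mean daily BG.** Take D = 18, f = 0 and SD 50 (the documents give an SD for fasting BG only). A 4-point mean (fasting, pre-lunch, pre-dinner, bedtime) shows 3/4 × 18 = 13.5, with noncentrality (18 − 13.5)/6.32 = 0.71 and probability 0.11. A 5-point mean that adds an unchanged 3 AM reading shows 3/5 × 18 = 10.8, with noncentrality 1.14 and probability 0.20. With SD 40 the 4-point figure is 0.14.

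**Step 5. What secondary outcome 1 can say.** With SD 50 again assumed, an observed daytime difference of 12 has a 95% CI of 12 ± 12.5, or −0.5 to 24.5. That is not significant at 0.05, yet the interval contains 18.

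**Step 6. Cost of requiring both results.** If the true difference is 0 and SD is 50 for both measures, the chance that both upper limits fall below 18 lies between 0.809 × 0.809 = 0.65 (independent) and 0.81 (fully correlated).

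**The case against.** The strongest reply is that this is mostly a consequence of VII naming a different primary outcome from IV.b. If mean daily BG becomes the tested endpoint, step 4 shows that the problem largely goes away. That stands, and it limits the point to the test as VII now writes it.

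Second, daytime BG is not ignored. Secondary outcome 1 covers it, and at SD 50 (assumed) a two-sided test would detect a true daytime loss of 18 mg/dL with about 81% power. That also stands. A reader might infer that nothing in the plan could expose a daytime loss, and the documents do not support that. What the plan lacks is a margin for daytime BG, or a statement of how it bears on the conclusion.

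Third, the real contrast may be smaller by day and larger by night than step 2 suggests. Fifteen units is a ceiling; Table 1 reports mean supplemental insulin of 5-9 units a day in earlier basal bolus arms. Overnight, IV.a has Group 1 corrected at bedtime above 140, while IV.d says above 220. The Group 2 supplemental insulin text mentions meals only, yet Group 2 has a bedtime table. Patients who cannot eat are corrected every 6 hours. So the finding that bedtime doses differ only at 221-260 holds by the tables, not by every passage.

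Fourth, pre-dinner BG is also a titration target, so a daytime mean is itself partly pulled toward a common value. This is fair: the daytime mean is a better test than fasting BG, not an untouched one.

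**Conclusion.** The concern holds for the non-inferiority test as written in VII. Fasting BG is a weak measure of what pre-meal correction does: with 125 per group and SD 50, a daytime loss as large as the margin would be declared non-inferior 57% to 81% of the time at 25% to 0% carry-over, and 29% at 50%. These figures rest on the assumed carry-over, on SD 50, and on bedtime correction following the tables.

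Two stronger readings are tempting and not supported. A reader might infer that a daytime loss of any size would pass on fasting BG. That needs carry-over of exactly zero, which the documents do not give. The earlier trial varied bedtime correction only, so it says nothing about carry-over from three pre-meal doses; it also reported no change in mean daily or pre-meal glucose. A reader might also infer that mean daily BG would let through daytime losses of 24 mg/dL (4-point, 18/0.75) or 30 mg/dL (5-point, 18/0.6), since these dilute to 18. But the confidence limit, not the point estimate, has to clear the margin, and at a true difference of 18 non-inferiority is declared only 2.5% of the time.

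This should be addressed before the analysis is fixed. It does not invalidate the trial.

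**What to change.** In VII, add a key supportive analysis: the per-patient mean of pre-lunch, pre-dinner and bedtime BG on treatment, with the two-sided 95% CI of the difference between arms shown against 18 mg/dL. State the assumed SD of this mean and the resulting power. Add that a non-inferiority result on fasting BG will be reported as a finding on fasting BG, and described as covering daytime control only if this second upper limit is also below 18 mg/dL.

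The readings are nearly all in the plan already. Two details need settling: the monitoring text asks for bedtime and/or 3 AM readings in Group 1 but for both in Group 2, and the analysis must say how six-hourly readings in patients who are not eating are assigned.

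The cost is that the broader claim becomes harder to reach, at about 65-81% instead of 81% under the assumptions in step 6. If the daytime condition is made binding, it acts as a co-primary; whether to do so is the sponsor's choice. The sample size for the fasting test does not change.

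Separately, IV.b and VII must be reconciled on the primary endpoint; if mean daily BG is chosen, it needs its own SD. The statements on bedtime correction in IV.a, the IV.d text, the Group 2 supplemental insulin text and the two bedtime tables must also be reconciled.

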##### **IV.b. Primary and Secondary Outcomes:**

The primary outcome of the study is to compare differences in mean daily BG levels between patients receiving insulin supplementation for correction of hyperglycemia (BG > 140 mg/dL) compared to those without insulin supplementation except for correction of severe hyperglycemia (BG > 260 mg/dL).

Secondary outcomes include differences between treatment groups in any of the following measures: 1) mean BG before meals, bedtime and 3 AM; 2) number of BG within target; 3) number of hypoglycemia (BG < 70 mg/dl); hyperglycemia (BG > 260 mg/dL during the day or BG>350 mg/dl at bedtime); 4) daily dose of insulin; 5) length of hospital stay and mortality; 6) hospital complications (nosocomial infections, pneumonia, bacteremia, respiratory failure, and acute kidney injury [rise of serum creatinine >0.5 mg/dL (or 50%) of baseline value]), 7) hypoglycemia symptom assessment in both groups.

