**Group 1. Basal bolus regimen with corrective doses of rapid-acting insulin prior to meals.**

**Patients Treated with Insulin Prior to Admission**

- Subjects receiving insulin therapy will receive 80% of the total daily outpatient insulin dose. For subjects receiving glargine, detemir, regular, lispro, glulisine or aspart, the total daily insulin dose prior to admission will be switched to basal insulin (glargine or detemir)/ meal time insulin (aspart/lispro) combination on a unit-for-unit basis.
- Half of total daily dose will be given as basal insulin (glargine or detemir) insulin and half as meal time insulin (aspart/lispro) insulin.
- Basal insulin (glargine or detemir) insulin will be given once daily, at the same time of the day.
- Patients will receive the full-dose of basal insulin (glargine or detemir) (even if NPO) the day of surgery or diagnostic procedure(s).
- Meal time insulin (aspart/ lispro) insulin will be given in three equally divided doses before each meal. To prevent hypoglycemia, if a subject is not able to eat, the dose of meal time insulin (aspart/lispro) will be held.

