### **Patients Treated with Oral Agents Prior to Admission**

- Oral antidiabetic drugs (sulfonylureas, repaglinide, nateglinide, metformin, pioglitazone, DPP4 inhibitors) and non-insulin injected antidiabetic drugs (pramlinitide, exenatide, liraglutide) will be discontinued on admission.
- **Starting total daily insulin dose:**
  - 0.4 units per kilogram of body weight per day when the blood glucose concentration at randomization is between 140-200 mg/dL.
  - 0.5 units per kilogram of body weight per day blood glucose concentration at randomization is between 201-400 mg/dL
  - The starting insulin TDD will be reduced to 0.3 units per kg in patients  $\geq 70$  years of age and/or with an eGFR  $< 60$  ml/min.
- Half of total daily dose will be given as basal insulin (glargine or detemir) and half as meal time insulin (aspart/lispro).
- Basal insulin (glargine or detemir) will be given once daily, at the same time of the day.
- Patients will receive the full-dose of basal insulin (glargine or detemir) insulin (even if NPO) the day of surgery or diagnostic procedure(s).
- Meal time insulin (aspart/lispro) will be given in three equally divided doses before each meal. To prevent hypoglycemia, if a subject is not able to eat, the dose of aspart/lispro will be held.

**Supplemental insulin.** Aspart/lispro insulin will be administered following the “supplemental insulin scale” protocol.

- If a patient is able and expected to eat all or most of his/her meals, supplemental aspart or lispro insulin will be administered before each meal and at bedtime following the “usual” dose of the supplemental insulin scale protocol.
- If a patient is not able to eat, supplemental aspart or lispro insulin will be administered every 6 hours following the “sensitive” dose of the supplemental insulin scale protocol.

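### No baseline covariate is pre-specified for daily insulin dose, although the protocol calculates each patient's starting dose from baseline data; the cost is precision, not bias

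*Combined protocol and SAP*

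**What the plan says.** Section IV.b lists "4) daily dose of insulin" among the secondary outcomes. It gives no unit and does not say whether total, scheduled or supplemental insulin is meant.

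Section VII (Data Analysis) plans one-way ANOVA or linear models for the primary outcome, followed by repeated-measures versions. It then adds: "Similar analyses will be conducted for continuous secondary outcomes". No covariate is named there or elsewhere.

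Section IV.d ties the starting total daily dose to facts known at baseline:

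- Prior insulin users: "Subjects receiving insulin therapy will receive 80% of the total daily outpatient insulin dose".
- Insulin-naive patients, lower glucose band (Group 1 wording): "0.4 units per kilogram of body weight per day when the blood glucose concentration at randomization is between 140-200 mg/dL". The factor is 0.5 U/kg in the higher band and 0.3 U/kg for patients aged 70 or over or with eGFR below 60.

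Both arms then titrate by the same percentage steps. Group 2 receives correction insulin only above 260 mg/dL. Table 1 shows mean supplemental doses of 5 to 9 U/day within mean totals of 32 to 57 U/day in earlier basal bolus arms.

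**The concern.** A patient's starting dose reflects body weight, home insulin dose, age, renal function and glucose, none of which depends on the arm. Titration then works in percentages of the current dose, so differences present at the start tend to carry forward. An analysis without the starting dose leaves all that spread in the error term, while the arms are expected to differ by only a few units a day.

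The dose result affects how the glucose result is read: did withholding correction lower insulin exposure, or did scheduled insulin rise to replace it? The background in the research objectives section already cites a finding of no difference in total daily dose, from the earlier bedtime-correction trial, in support of the hypothesis. An imprecise null here could be used in the same way. A total alone also could not show whether insulin had shifted from supplemental to scheduled.

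**Working it through.** **1. The plan's own figure.** Section VII sizes the primary comparison only. Inputs: "We set the equivalence margin in our non-inferiority hypothesis for comparing treatment effect as 18 mg/dL (1 mmol/l"); "we anticipate a standard deviation of mean fasting BG~50 mg/dL"; "Here we conservatively set the significance level as 0.025"; and "With a one-sided, two-sample t-test, 123 subjects would be required for each group to achieve 80% power to detect non-inferiority".

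Normal approximation: n = 2 × (1.960 + 0.842)² × 50² / 18² = 121.1, so 122 per arm. The noncentral t calculation gives 123 (power 80.3%). The stated 123 reproduces. No figure is given for insulin dose.

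**2. Size of the difference to be detected.** Supplemental dose in Table 1, weighted by trial size:

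(65×5 + 104×9 + 206×6 + 144×7 + 67×8) / 586 = 4041 / 586 = 6.9 U/day.

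The mean total weighted the same way is 23241 / 586 = 39.7 U/day. I use 7 U/day. It is close to an upper value for an average patient, because it assumes no supplements in Group 2 and no offset through titration.

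**3. Spread created by the dosing rule.** At assumed weights of 60 and 120 kg, insulin-naive patients could start anywhere from 0.3 × 60 = 18 to 0.5 × 120 = 60 U/day. Under an assumed mix (40% prior insulin users; mean weight 92 kg, SD 15-25; mean home dose 50 units, SD 25-35), the SD of the starting dose alone is about 15 to 20 U/day. The documents give no SD of insulin dose, so I take 15 to 30 U/day for the outcome.

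**4. Unadjusted precision.** SE = SD × √(2/125). The 95% CI half-width is 1.96 × SE, and the difference detectable with 80% power is 2.80 × SE.

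| Assumed SD (U/day) | Half-width | Detectable difference |
|---|---|---|
| 15 | 3.7 | 5.3 |
| 20 | 5.0 | 7.1 |
| 25 | 6.2 | 8.9 |
| 30 | 7.4 | 10.6 |

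**5. Effect of adjustment.** With a covariate correlated ρ with the outcome, the residual SD is SD × √(1 − ρ²). Variance falls by 9% at ρ = 0.3, 25% at 0.5 and 49% at 0.7. Power for 7 U/day, 125 per arm, two-sided 0.05 (noncentral t):

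| SD | Unadjusted | ρ = 0.3 | ρ = 0.5 | ρ = 0.7 |
|---|---|---|---|---|
| 15 | 96% | 97% | 99% | >99% |
| 20 | 79% | 82% | 89% | 97% |
| 25 | 60% | 64% | 72% | 87% |
| 30 | 45% | 49% | 56% | 73% |

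At the ends of the Table 1 range, unadjusted power over SD 15 to 30 runs from 75% down to 26% for 5 U/day, and from above 99% down to 66% for 9 U/day. For 5 U/day at SD 25, it is 35% unadjusted, 44% at ρ = 0.5 and 60% at ρ = 0.7. For 9 U/day at SD 15 there is nothing left to gain.

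**6. Is the prescribed starting dose usable as it stands?** For insulin-naive patients, the Group 1 text selects the dose band by glucose at randomization. The Group 2 text refers to admission and/or randomization glucose for the lower band, and to admission and/or mean glucose for the higher band. Read literally, the prescribed starting dose could depend on the arm. A covariate must not, so it has to be recalculated by one formula.

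**The case against.** A reader might infer that the plan commits to an unadjusted comparison of raw units, and that body weight and home dose will swamp any difference between arms. The documents support neither reading. Section IV.b names no unit; only the background data are in units/day. A linear model can carry baseline terms, so this is an omission and not a decision against adjustment. Nor is a single pooled total stated: the background reports total and supplemental insulin separately for earlier trials, although Section IV.b does not promise that split here. Swamping is not shown either. At SD 15 to 20, unadjusted power for 7 U/day is 96% to 79%, and the primary endpoint itself was designed for 80%.

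The correlation is open to challenge too. Titration steps are daily, and four successive 20% increases multiply the basal dose by 1.2⁴ = 2.07. Meal-time insulin is held when a patient cannot eat, and physicians may change doses at their discretion. All of this adds variation after baseline. At ρ = 0.3 the gain is only 1 to 4 points in the table above. Proportional titration argues for a higher value, but the documents do not establish one.

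It would also be too strong to say that the arms can differ only by the supplemental dose. Supplements in Group 2 and basal titration can narrow or reverse the gap. If the true difference in total dose is near zero, no covariate will show whether insulin moved from supplemental to scheduled; the separate reporting does that.

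These points limit the size of the concern. They do not remove the case for naming the covariate in advance: it costs almost nothing, and leaving it open allows the choice of model to be made after the data are seen.

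**Conclusion.** The point holds as a low-cost improvement to one secondary outcome. Section VII pre-specifies no baseline covariate for insulin dose, although the protocol supplies an obvious one. Randomization keeps the unadjusted comparison unbiased; what is lost is precision. The primary endpoint and its sample size are unaffected.

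For 7 U/day, the gain at ρ = 0.5 is 3 points at SD 15 and 10 to 12 points at SD 20 to 30. At ρ = 0.7 it is 18 to 28 points for SD 20 to 30. It is negligible where unadjusted power is already near 100%. These figures rest on an assumed SD, an assumed correlation and an effect close to the full supplemental dose. The absence of a stated split between scheduled and supplemental insulin is a separate gap, and it bears more directly on whether insulin was shifted between the two.

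**What to change.** In Section VII, state that mean daily insulin dose (units/day) will be compared by a linear model with treatment arm and starting total daily dose as covariate, with the same covariate in the repeated-measures model. Define the covariate as a quantity computed for analysis only, from pre-randomization data (home insulin dose, or weight, age, eGFR and glucose), by the same formula in both arms. The differing glucose wording in the Group 1 and Group 2 starting-dose rules should be reconciled.

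In Sections IV.b and VII, state the unit and report scheduled (basal plus prandial), supplemental and total insulin separately.

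The cost is wording, one degree of freedom and recalculation of the covariate from data already collected. No dosing rule and no sample size changes.
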